Additional Exploratory Analyses: 1) Determine if aripiprazole as an add-on therapy is associated with a greater reduction in manic and depressive symptoms than placebo therapy in outpatients with BPD or Schizoaffective Disorder (Bipolar Type) and AUD. 2) Determine whether changes in alcohol craving and mood occur before or after changes in alcohol use with aripiprazole. 3) Determine if impulsivity decreases with aripiprazole as compared to placebo and examine relationships between change in impulsivity and change in alcohol consumption. 4) Assess rates of attrition, safety and tolerability of aripiprazole. 5) Examine genotype as a predictor of response to aripiprazole. 6) Explore safety, tolerability and efficacy of an increase in aripiprazole from 15 mg to 30 mg at week 12 for those with at least one heavy drinking day at week 12. 7) Determine if inflammation decreases with aripiprazole as compared to placebo and whether change in an inflammatory biomarker is associated with change in clinical outcomes.

2. Background:

Drug and alcohol abuse are common in persons with BPD.¹⁻⁴ In a community-based study, persons with bipolar I disorder had a 46% lifetime prevalence of alcohol-related disorders compared to 14% in the population as a whole.⁵ Odds ratio of alcohol dependence is 5.5 for bipolar I disorder and 3.1 for bipolar II disorder. BPD is also much more common in people with alcohol dependence than the general population, with a 6% prevalence in men (odds ratio 12) and 7% in women (odds ratio 5).⁶ Although disulfiram is effective for highly motivated patients, lack of adherence and safety concerns limit its use.⁷⁻⁹ Acamprosate is an effective

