A urine sample for drug screen and pregnancy test (if applicable), psychiatrist assessment, physical exam, collection of weight and vitals can be completed at either Baseline 1 or Baseline 2.

For Baseline 2 (~1.5 hours), recent depressive symptoms will be assessed via the Inventory of Depressive Symptomatology—Self-Report^{37,40} 30-item version (IDS-SR₃₀), and drinking behavior will be characterized using the Penn Alcohol Craving Scale³¹ (PACS), safety and side effects will be assessed with the Psychobiology of Recovery in Depression III - Somatic Symptom Scale⁴² (PRD-III), the Abnormal Involuntary Movement Scale⁴³ (AIMS), Barnes Akathisia Scale⁴⁴ (BAS) and Simpson-Angus Scale⁴⁵ (SAS), and Go/No-go task.^{46, 47}. The Treatment Impressions Inventory (TII) is a survey about the participants' feelings and impressions towards medical treatment. The TLFB will be repeated to account for drinking behavior since the last visit and CIWA-Ar will account for any withdrawal symptoms. The aripiprazole or placebo capsules will be initiated at 2 mg/day in the morning, increased (if well tolerated) to 5 mg at week 1, 10 mg at week 2 and 15 mg/day (or equivalent placebo) at week 3. Participants taking concomitant medications that are strong inhibitors of the 3A4 or 2D6 isoenzymes will be titrated to a maximum dose of 10 mg/day. Strong CYP3A4 inhibitors are the following: Atazanavir, Boceprevir, Clarithromycin, Cobicistat, Conivaptan, Curcumin, Danazol, Danoprevir, Darunavir, Delavirdine, Diltiazem, Ditiocarb, Econazole, Efavirenz, Elvitegravir, Ergotamine, Idelalisib, Indinavir, Itraconazole, Ketoconazole, Lonafarnib, Loperamide, Lopinavir, Methimazole, Midostaurin, Naloxone, Nefazodone, Nelfinavir, Nilotinib, Posaconazole, Ribociclib, Ritonavir, Saquinavir, Stiripentol, Telaprevir, Telithromycin, Terfenadine, Tipranavir, Troleandomycin, Voriconazole. Strong CYP2D6 inhibitors are the following: Thioridazine, Paroxetine, Cinacalcet, Bupropion, Methotriptane, Fluoxetine, Midostaurin, Propafenone, Glycerol phenylbutyrate, Halofantrine, Cisapride, Dacomitinib, Orphenadrine, Quinidine. For patients taking strong CYP3A4 inducers, the aripiprazole or placebo capsules will be initiated at 4 mg/day in the morning, increased (if well tolerated) to 10 mg at week 1, 20 mg at week 2 and 30 mg/day (or equivalent placebo) at week 3. Participants taking strong CYP3A4 inducers will not be enrolled in the extension phase.

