Strong CYP3A4 inducers are the following: Nevirapine, Rifabutin, Rifampicin, Carbamazepine, Fosphenytoin, Pentobarbital, Phenobarbital, Phenytoin, Primidone, Rifapentine, Enzalutamide, Lumacaftor, St. John's Wort, Mitotane, Apalutamide, and Quinine.

Week 1, 2, 3, 5, 7, 9, 10, 11 (~2 hours each): Subjects will complete the YMRS, HRSD₁₇, CIWA-Ar, TLFB, IDS-SR₃₀, PACS, PRD-III, AIMS, BAS, SAS, and a urine sample will be collected for a drug screen. Subjects will meet with the psychiatrist for weekly assessment and vitals will be collected. In addition, all participants will receive one-hour sessions of manual-driven Medical Management (MM), specifically designed for persons with BPD and substance abuse, provided by an experienced therapist.

Week 4, 8 (~2.5 hours each): Subjects will complete the YMRS, HRSD₁₇, CIWA-Ar, TLFB, IDS-SR₃₀, PACS, PRD-III, AIMS, BAS, SAS, MM, and a urine sample will be collected for a drug screen and pregnancy test. Subjects will meet with the psychiatrist for weekly assessment and vitals will be collected. Blood will be drawn for CBC, CMP, GGT, and CDT.

Week 6 (~2.5 hours): Subjects will complete the YMRS, HRSD₁₇, CIWA-Ar, TLFB, IDS-SR₃₀, PACS, PRD-III, AIMS, BAS, SAS, GNG, MM, and a urine sample will be collected for a drug screen. Subjects will meet with the psychiatrist for weekly assessment and vitals will be collected.

Week 12 (~3.5 hours): Subjects will complete the YMRS, HRSD₁₇, CIWA-Ar, TLFB, IDS-SR₃₀, PACS, PRD-III, AIMS, BAS, SAS, GNG, BIS-11, MM, and a urine sample will be collected for a drug screen and pregnancy test. Subjects will meet with the psychiatrist for weekly assessment and vitals will be collected. Blood will be drawn for CBC, CMP, hs-CRP, GGT, CDT, lipids, and for aripiprazole levels. An exit survey will also be administered to participants evaluating their perception of in-person vs. virtual study visits. In the event of early discontinuation, the survey will be administered at the last available study visit.

At the end of the week 12 treatment phase, participants in both treatment arms who are taking 15 mg/day of aripiprazole (or placebo) and with at least one heavy drinking day will be asked to continue in a 4-week extension phase. Participants taking 3A4 or 2D6 inhibitors will be excluded from this phase. Those in the active treatment group will be increased to 30 mg/day while those in the placebo arm will remain on placebo.

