4) *Assess rates of attrition, safety and tolerability of aripiprazole.* Length of time in the study in weeks will be compared between groups using Cox proportional hazards regression. Scores on the PRD-III, AIMS, BAS and SAS will be compared between-groups as with the Primary Aim above.

5) *Examine genotype as a predictor of response to aripiprazole.* The purpose of this analysis is to identify whether genotype (e.g. 1438A polymorphism in the promoter region of the 5-HT2A receptor, LL compared with the LS/SS of the 5-HTLPR promoter region of the 5-HTT) is a moderator of treatment effect. Treatment effect is determined by treatment group, main effect and treatment group by time interaction effect estimated from the random regression model described for the primary aim. The potential moderator of genotype will be included in the random regression model for the primary outcome along with variable by treatment group interaction and variable by treatment group by time interaction. Significance for either interaction term would indicate that the variable is a moderator.

6) *Explore safety, tolerability and efficacy of an increase in aripiprazole from 15 mg to 30 mg at week 16 for those with at least one drinking day at week 12.* All lab values and other safety measures will be compared between treatment groups at week 16 using t-test or chi-square test, as appropriate. Scores on outcomes measures including alcohol use (e.g. heavy drinking days) and side effect scales (e.g. BAS) will be compared between groups at week 16 using analysis of covariance. Week 12 value of the outcome will be the covariate.

7) *Determine if inflammation decreases with aripiprazole as compared to placebo and whether change in an inflammatory biomarker is associated with change in clinical outcomes.* Analysis described for Exploratory Aim 3 (above) will be used with hs-CRP data to test this aim.

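### Exploratory Aim 6 asks what the step from 15 to 30 mg does, but the planned week-16 ANCOVA against placebo cannot isolate the step and can credit it with part of a continuing 15 mg effect

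*Combined protocol and SAP*

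**What the plan says.** The aim appears twice. Section 1, item 6 of the exploratory analyses, reads "Explore safety, tolerability and efficacy of an increase in aripiprazole from 15 mg to 30 mg at week 12". Section 14, item 6, reads "Explore safety, tolerability and efficacy of an increase in aripiprazole from 15 mg to 30 mg at week 16". Both ask about the increase itself.

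Section 4 (end of the week-12 visit) defines entry as "participants in both treatment arms who are taking 15 mg/day of aripiprazole (or placebo) and with at least one heavy drinking day". It then sets the treatment: "Those in the active treatment group will be increased to 30 mg/day while those in the placebo arm will remain on placebo". Two groups whose dose might have stayed unchanged do not enter: "Participants taking 3A4 or 2D6 inhibitors will be excluded from this phase", and "Participants taking strong CYP3A4 inducers will not be enrolled in the extension phase". No entrant is therefore planned to continue on 15 mg.

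For the analysis, Section 14 says that outcome and side-effect scores "will be compared between groups at week 16 using analysis of covariance. Week 12 value of the outcome will be the covariate". No other covariate is named for this analysis. Laboratory values and other safety measures get an unadjusted t-test or chi-square test at week 16. Nothing in the plan limits the conclusion to drug versus placebo.

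The entry rule is not uniform. Sections 3 and 14 require any drinking day at week 12; Sections 1 and 4 require a heavy drinking day. The two statements of the aim also date the increase differently, at week 12 and at week 16.

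**The concern.** A question about a dose step needs a comparison with the unchanged dose, and the extension has none. The week-12 covariate may seem to supply one, as if adjusting for it removed whatever 15 mg had already achieved. It does so only in part.

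Week 12 is a single noisy reading of a person's usual level, taken while the drug is acting. An active and a placebo entrant with the same week-12 value do not have the same underlying level. By week 16 each drifts back toward their own arm's mean, and the active mean is lower if 15 mg works. The ANCOVA reads that drift as a group difference, and the aim as worded would call it an effect of the increase.

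At stake is the interpretation of a prespecified aim with its own four-week phase. Side-effect scales analysed the same way, such as the BAS, carry the same misattribution in the unfavourable direction. The unadjusted safety comparisons credit the increase with the whole drug-placebo difference present at week 16.

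**Working it through.** **The plan's own figure.** Section 14 assumes an effect of 0.5 SD, 80% power and two-sided alpha 0.05. The t-based calculation gives 63.8, so 64 per arm and 128 in total; 128 / 0.97 = 131.96, so 132. Both figures reproduce. No figure is stated for the extension.

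**Inputs.** d = 0.5 SD is the Section 14 planning value, not a forecast for week-12 drinkers. The correlation r between weeks 12 and 16 and the number of entrants are not given; the values below are assumptions.

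**Step 1: formula.** Let G = 1 for active and 0 for placebo, with SD 1 at both times, the same 15 mg effect -d at weeks 12 and 16, and no effect of the increase.

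E[Y16 | Y12, G] = μ - dG + r(Y12 - μ + dG) = (1-r)μ + r·Y12 - (1-r)d·G.

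The ANCOVA group coefficient is -(1-r)d. A correct answer about the increase would be 0.

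**Step 2: equal response, d = 0.5.**

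| r | (1-r) × 0.5 |
|---|---|
| 0.5 | 0.25 SD |
| 0.6 | 0.20 SD |
| 0.7 | 0.15 SD |
| 0.8 | 0.10 SD |

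Simulation reproduces these values with and without selection on week 12, and gives 0 when d = 0. Selection does make the groups unequal: with entry 0.5 SD below the placebo mean and d = 0.5, 69% of placebo and 50% of active patients enter.

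**Step 3: unequal response, mean effect still 0.5 SD.** Suppose half the active arm respond by 1 SD and half not at all. Without selection, the active week-12 variance is 1 + 0.25 and its covariance with week 16 is r + 0.25. The pooled slope is (2r + 0.25)/2.25, and the coefficient is -0.5 × (1 - slope). At r = 0.6 the slope is 1.45/2.25 = 0.644, giving -0.18 SD.

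Selecting week-12 drinkers removes responders and shrinks this. With entry 0.5 SD below the placebo mean, the simulated artefact is 0.12 SD at r = 0.6 and 0.06 SD at r = 0.8. A stricter cut gives less: about 0.11 to 0.04 SD over r = 0.5 to 0.8. If only a quarter respond, by 2 SD, it is about 0.01 to 0.02 SD.

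**Step 4: count scale.** Take heavy drinking days over an assumed 7 days, entry at one or more, and the same logit effect of -0.5 at both times. The ANCOVA shows a false -0.29 days when r = 0.59 (week-12 difference -0.69) and -0.10 days when r = 0.82 (week-12 difference -0.52).

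**Step 5: chance of p < 0.05 with an ineffective increase, equal response, d = 0.5.**

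| Entrants per arm (assumed) | r = 0.4 | r = 0.6 | r = 0.8 |
|---|---|---|---|
| 20 | 15% | 11% | 8% |
| 40 | 30% | 19% | 11% |

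With d = 0 it stays near 5%.

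**Step 6: would a change score do better?** Change from week 12 itself does not cure the problem, because week 12 selects the entrants: -0.12 SD at d = 0.5, r = 0.6. Change from the mean of weeks 9-11 is near 0 under a constant effect with exchangeable correlation, and about -0.03 SD with a random intercept plus AR(1) errors.

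It fails if the 15 mg effect is still growing. Suppose the effect rises linearly to 0.5 SD at week 12 and continues at 0.5/12 per week. From week 10 (the midpoint of 9-11) to week 16 the false benefit is 6 × 0.5/12 = 0.25 SD. Averaging weeks 14 and 16 (midpoint 15), it is 5 × 0.5/12 = 0.21 SD. The ANCOVA gives (16/12) × 0.5 - 0.5r, which is 0.42 to 0.27 SD for r = 0.5 to 0.8.

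**The case against.** The other side has four fair points.

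- **Size.** A reader might infer that 0.25 to 0.10 SD is the expected bias. The documents do not support that. Entry requires continued drinking at week 12, which favours 15 mg non-responders, and Step 3 shows how quickly the artefact falls. The equal-response figures are an upper case. It does not vanish by rule, though: one qualifying day is enough to enter, and partial responders can have one.
- **Weight.** This is the sixth exploratory item, worded as exploration, with no decision rule. The primary and secondary aims are unaffected. A reader might also infer that the extension will usually show a significant false benefit. It will not: Step 5 gives 8% to 30%, and that under equal response at d = 0.5.
- **Remedy.** A reader might infer that replacing the ANCOVA with a change score would isolate the increase. It would not. Section 14 models random slopes and a group-by-time term, so the plan itself allows a drug effect that changes over time, and Step 6 shows the cost. A change score also subtracts the existing 15 mg effect, so it does not estimate aripiprazole versus placebo. The two analyses answer different questions and need separate labels.
- **Population.** The entry rule is unresolved, so the simulated cuts are illustrative.

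None of this restores the missing comparator. The aim is still worded as the effect of the increase, and the planned contrast does not estimate that.

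**Conclusion.** The concern holds as a limit on interpretation. No entrant is planned to stay on 15 mg, so neither the ANCOVA nor any other analysis of the two planned groups isolates the increase without a further assumption. The ANCOVA can credit an increase that does nothing with up to (1-r)d.

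The size rests on the planning value d = 0.5, an assumed r of 0.5 to 0.8 and the pattern of response: 0.25 to 0.10 SD under equal response, about 0.11 to 0.04 SD if half respond by 1 SD (slightly more under a looser entry cut), and near zero if non-responders dominate or 15 mg has no effect. The artefact needs a 15 mg effect that persists among entrants and r below 1. The change is worth making because it is nearly free; it is not a threat to the trial's main conclusions.

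**What to change.** 1. **Restate the conclusion in Section 14, Aim 6.** Keep the week-16 between-group comparison. State that it estimates aripiprazole (continued and increased) versus placebo among week-12 drinkers, at a given week-12 value where the ANCOVA is used. State that it will not be reported as the efficacy or tolerability of the increase itself, and apply the same wording to the side-effect scales and unadjusted safety comparisons. Note that entry follows randomisation, so the groups compared are no longer the randomised groups.

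2. **Add one supportive analysis of the increase.** Compare arms on within-person change from the mean of weeks 9-11 to week 16, with week 14 added if wanted. The TLFB and the rating scales are already scheduled at all these visits. Weeks 9-11 must not contribute to entry, so state the window in which the qualifying day is counted. Label the result as valid only if the 15 mg effect would otherwise have stayed constant, and say that it can show 0.21 to 0.25 SD of false benefit if an effect reaching 0.5 SD at week 12 is still growing linearly.

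3. **Reconcile the text.** Sections 3 and 14 (any drinking day) conflict with Sections 1 and 4 (heavy drinking day), and this defines the population analysed. The week-12 and week-16 datings of the increase must also agree.

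The cost is wording in the analysis plan, a more modest claim, and lower precision for the supportive contrast. No new visits, data or randomisation are needed.
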